### **9.5.2 Schedule of Procedures/Assessments**

#### **9.5.2.1 Schedule of Procedures/Assessments**

[Table 5](#) presents the schedule of procedures/assessments for the Randomization Phase of the study.

[Table 6](#) presents the schedule of procedures/assessments for the Extension Phase of the study.

**Table 7** presents the schedule of procedures/assessments for the Optional Lenvatinib Crossover Treatment Phase of the study.

**Table 5 Schedule of Assessments in Study E7080-G000-230 – Randomization Phase**

Phase	Prerandomization		Randomization a (All cycles are 21 days in duration)																	
	Screening b	Baseline c	Treatment d																Off-Tx	Follow-up
Period	1	2	3	4	5	6	7	8	9	10	11	12	13	14	15	16	17	18+		
Visit	1	2	3	4	5	6	7	8	9	10	11	12	13	14	15	16	17	18+		
Cycle			Cycle 1			Cycle 2			Cycle 3			Cycle 4			Cycle 5			Cycle 6-X		
Day	-28 to -2	-1	1	8	15	1	8	15	1	8	15	1	8	15	1	8	15	1		
Procedures/Assessments																				
Informed consent	X																			
Inclusion/exclusion	X	X																		
Randomization (IVRS)			X																	
Demographic data	X																			
Medical/surgical history	X	X																		
Prior medication/ procedures	X	X																		
Pregnancy test e	X	X				X			X			X			X			X	X	
Lansky play score/ Karnofsky PS f	X	X	X			X			X			X			X			X		
TNM Staging	X																			
Physical examination g	X	X	X		X	X		X	X			X			X			X	X	
Vital signs h	X	X	X	X i	X	X		X	X			X			X			X	X	
12-lead ECG j	X		X		X													X	X	
Echocardiogram or MUGA scan k	X		Performed every 16±2 weeks following the first dose of study drug or sooner, if clinically indicated															X		
Clinical chemistry and hematology l	X	X			X	X		X	X			X			X			X	X	
Urine dipstick testing m	X	X			X	X		X	X			X			X			X	X	
PK blood samples n			X		X															

**Table 5 Schedule of Assessments in Study E7080-G000-230 – Randomization Phase**

Phase	Prerandomization		Randomization a (All cycles are 21 days in duration)																		
	Screening b	Baseline c	Treatment d																Off-Tx	Follow-up	
Period	Visit	1	2	3	4	5	6	7	8	9	10	11	12	13	14	15	16	17	18+		
Visit			Cycle 1			Cycle 2			Cycle 3			Cycle 4			Cycle 5			Cycle 6-X			
Day	-28 to -2	-1	1	8	15	1	8	15	1	8	15	1	8	15	1	8	15	1			
Procedures/Assessments			Arm A: Combination of lenvatinib (QD) + ifosfamide + etoposide (Days 1-3 of Cycles 1-5 only) [based on BSA calculations at Day 1 of each Cycle]; after Cycle 5 subjects will receive lenvatinib alone. Arm B: Ifosfamide + etoposide (Days 1-3 of Cycles 1-5 only) [based on BSA calculations at Day 1 of each Cycle]																		
Study treatment o			X																		
Palatability Questionnaire p			X																		
Tumor assessments: CT/MRI q	X		CT chest and CT/MRI of other areas of known disease at Screening plus any areas of newly suspected disease should be performed every 6±1 week after the date of randomization or sooner if clinically indicated until Week 18±1 week, then every 9±1 weeks until Week 54±1 week. Thereafter, to be performed every 12±2 weeks until documentation of PD.																	X q	
Brain CT/MRI r	X		Brain scans will be performed at screening as clinically indicated, and thereafter during treatment if clinically indicated. For subjects with protocol-eligible, treated brain metastases at Screening, brain scans should be performed at all tumor assessment time points.																		
Height s		X	X												X					X	X
Tanner Stage t		X																			X
Proximal tibial growth plate x-ray s		X																			X
Dental examination s		X	X as per standard of care or at least annually																		X
HRQoL u		X	HRQoL will be collected on C2D1, C3D1, Week 18, C8D1, and C18D1.																		X u
Pharmacodynamic biomarkers v		X			X	X									X					X	
Archival tumor block or slides w			X																		
Survival x															X						X

**Table 5 Schedule of Assessments in Study E7080-G000-230 – Randomization Phase**

Phase	Prerandomization		Randomization a (All cycles are 21 days in duration)																	
	Screening b	Baseline c	Treatment d															Off-Tx	Follow-up	
Period	1	2	3	4	5	6	7	8	9	10	11	12	13	14	15	16	17	18+		
Visit	1	2	3	4	5	6	7	8	9	10	11	12	13	14	15	16	17	18+		
Cycle			Cycle 1			Cycle 2			Cycle 3			Cycle 4			Cycle 5			Cycle 6-X		
Day	-28 to -2	-1	1	8	15	1	8	15	1	8	15	1	8	15	1	8	15	1		
Procedures/Assessments																				
Concomitant medications y	Throughout																		X	
AEs/SAEs z	Throughout																		X	

AE = adverse event, BP = blood pressure, C1D1 = Cycle 1 Day 1, C1D2 = Cycle 1 Day 2, C1D8 = Cycle 1/Day 8, C1D15 = Cycle 1 Day 15, CR = complete response, CT = computerized tomography, h = hour, HR = heart rate, HRQoL = Health-Related Quality of Life, IV = intravenous, IVRS = Interactive Voice Response System, MRI = magnetic resonance imaging, MUGA = multiple-gated acquisition, PD = progressive disease/disease progression, PK = pharmacokinetics, PR = partial response, PS = performance score, RECIST 1.1 = Response Evaluation Criteria in Solid Tumors, version 1.1, RR = respiratory rate, SAE = serious adverse event, TNM = tumor-node-metastasis, Tx = treatment.

- During Cycle 1, efforts should be made to conduct study visits on the day scheduled ( $\pm 1$  day); from Cycle 2 onwards, efforts should be made to conduct study visits on the day scheduled ( $\pm 3$  days).
- The results of all screening assessments and evaluations must be completed and reviewed by the investigator prior to the Baseline Visit. Informed consent may be obtained up to 4 weeks prior to C1D1.
- Baseline assessments can be performed on Day -1 or on C1D1 prior to treatment.
- For subjects randomized to Arm A, subjects benefiting from study treatment in the opinion of the investigator will continue lenvatinib treatment until PD, intolerable toxicity, noncompliance with safety or efficacy assessments, voluntary discontinuation by the subject at any time, or study termination by the sponsor, whichever occurs first.
- A serum or urine pregnancy test will be performed at the Screening and Baseline Visits (or within 72 hours prior to the first dose of study medication), on Day 1 of each cycle from Cycle 2 onwards, and at the Off-treatment Visit in women of childbearing potential.
- A Lansky play score or Karnofsky performance status score will be obtained at the Screening, Baseline, and C1D1 Visit, and Day 1 of every subsequent cycle visit thereafter.
- A comprehensive physical examination (including a neurological examination) will be performed at the Screening and Baseline Visits (only if screening physical examination was performed  $>7$  days prior to C1D1), C1D15, C2D1, C2D15, and Day 1 visit of each subsequent cycle, and at the Off-treatment Visit. A symptom-directed physical examination will be performed on C1D1 and at any time during the study, as clinically indicated.

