**Table 5 Schedule of Assessments in Study E7080-G000-230 – Randomization Phase**

Phase	Prerandomization		Randomization a (All cycles are 21 days in duration)																	
	Screening b	Baseline c	Treatment d																Off-Tx	Follow-up
Period	1	2	3	4	5	6	7	8	9	10	11	12	13	14	15	16	17	18+		
Visit	1	2	3	4	5	6	7	8	9	10	11	12	13	14	15	16	17	18+		
Cycle			Cycle 1			Cycle 2			Cycle 3			Cycle 4			Cycle 5			Cycle 6-X		
Day	-28 to -2	-1	1	8	15	1	8	15	1	8	15	1	8	15	1	8	15	1		
Procedures/Assessments																				

- o. Subjects randomized to Arm A will continue to receive lenvatinib only after completion of 5 cycles with lenvatinib+ifosfamide+etoposide until progressive disease, unacceptable toxicity, subject request, study termination by the sponsor, subject noncompliance with safety or efficacy assessments, or withdrawal of consent. Subjects randomized to Arm B will be off-treatment after 5 cycles of ifosfamide+etoposide.
- p. All subjects who receive suspension formulation, with the exception of subjects using a nasogastric or gastrostomy tube, must complete the Palatability Questionnaire on C1D1 (or the subsequent visit). If the subject is unable to complete the questionnaire this must be done by their parents or their legal guardian.
- q. **Screening:** Tumor assessments of the chest, abdomen, pelvis, and other areas of known disease or newly suspected disease should be performed within 28 days prior to C1D1. Scans of the abdomen, pelvis, and other areas of the body may be done with MRI instead of CT, but evaluation of the chest should be done with CT. CT scans should be performed with iodinated IV contrast and MRI scans should be performed with IV gadolinium chelate.

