**Table 6 Schedule of Assessments in Study E7080-G000-230 – Extension Phase**

Phase	Extension a	
Period	Treatment Period a	Follow-up Period
Visit	98	99
Cycle	Cycle X +1 and beyond	Off-Tx Visit
Day	1	
Procedures/Assessments		
Pregnancy test b	X	X
Lansky play score/ Karnofsky PS c	X	X
Physical examination d	X	X
Vital signs e	X	X
12-lead ECG f	As clinically indicated	
Echocardiogram or MUGA scan g	As clinically indicated	
Clinical chemistry and hematology h	X	X
Urine dipstick testing i	X	X
Study treatment j	Arm A: Lenvatinib+ifosfamide+etoposide a Arm B: Ifosfamide + etoposide a	
Tumor assessments: CT/MRI k	After data cutoff for the primary analysis, tumor assessments may be performed as clinically indicated as per the institutional guidelines (but no less frequently than every 12 weeks), following the prevailing local standard of care.	
Brain CT/MRI l	After data cutoff for the primary analysis, tumor assessments may be performed as clinically indicated as per the institutional guidelines, following the prevailing local standard of care.	
Height m	To be checked every 4 cycles	X
Tanner Stage n		X
HRQoL o	X	X
Proximal Tibial growth plate x-ray p		X
Dental examinations q	X	X
Survival r	X	X
Concomitant medications s	Throughout	X
AEs/SAEs t	Throughout	X

AE = adverse event, CT = computerized tomography, ECG = electrocardiogram, HRQoL = Health-Related Quality of Life, ICL = imaging core laboratory, MRI = magnetic resonance imaging, MUGA = multiple-gated acquisition, PD = disease progression, PS = performance status, SAE = serious adverse event.

- a. In the Treatment Period, subjects still on study treatment following the completion of the Randomization Phase will continue to receive study treatment as outlined in [Section 9.1.2.1](#) until disease progression, development of unacceptable toxicity, subject request, withdrawal of consent, or discontinuation of study by the sponsor, whichever occurs first.
- b. A serum or urine pregnancy test will be performed on Day 1 of each cycle and at the Off-treatment Visit in women of childbearing potential.
- c. A Lansky play score or Karnofsky performance status score will be obtained at Day 1 of every cycle visit.

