- b. Subjects should meet all of the safety parameters listed in the inclusion criteria and none of the safety parameters listed in the exclusion criteria. If required locally, written informed consent will be obtained prior to assessment for Optional Lenvatinib Crossover treatment.
- c. A Lansky play score or Karnofsky performance status score will be obtained at Baseline, Day 1 of every cycle, and at the Off-treatment visit.
- d. A comprehensive physical examination (including a neurological examination) will be performed at Baseline, C1D15, C2D1, C2D15, Day 1 of each subsequent cycle, and at the Off-treatment Visit. A symptom-directed physical examination will be performed on C1D1 and at any time during the study, as clinically indicated.
- e. Assessments will include vital signs (resting BP, HR, RR, and body temperature) and weight. Blood pressure that is consistently above the 95th percentile for sex, age, and height/length for subjects <18 years old; or BP  $\geq$ 140/90 mmHg for subjects  $\geq$ 18 to 25 years old requires further evaluation. Refer to hypertension management guidelines in [Section 9.4.1.1.2](#).
- f. On Cycle 1 Day 8, subjects will have a telephone or clinic visit to assess for the development of early toxicity. Subjects will be provided with a BP cuff to monitor BP at home or can have the measurement done by a local healthcare provider, and will report the C1D8 measurement at telephone contact. An unscheduled visit can occur prior to C1D15 if deemed necessary by the investigator.
- g. Single 12-lead ECG. Baseline ECG may be performed within 28 days prior to C1D1. If possible, subjects must be in the recumbent position for a period of 5 minutes prior to the ECG. ECG should be conducted at C1D1, C2D1, D1 of every 4th cycle (i.e., C6, C10, C14, etc.), and at the Off-treatment visit. For high risk subjects (as defined in lenvatinib product label), conduct ECG in every cycle.
- h. An echocardiogram or MUGA scan is to be performed at Baseline, every 16 $\pm$ 2 weeks following first dose of study drug, and at the Off-Treatment visit, or sooner if clinically indicated. The Baseline ECHO/MUGA may be performed within 28 days prior to C1D1.

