#### 9.7.1.8.6 OTHER SAFETY ANALYSES

Descriptive summary statistics for LVEF changes from baseline will be calculated and summarized.

The shift of worst postbaseline proteinuria from Baseline will be summarized.

Thyroid-stimulating hormone values will be summarized in 2 categories ( $\leq$ ULN and >ULN).

Lansky play scores or Karnofsky Performance Status score scores will be summarized by shifts from Baseline to worst postbaseline visit.

Radiographic findings of proximal tibial growth plates will be listed and analyzed if appropriate.

Tooth formation abnormalities will be listed and analyzed if appropriate.

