## Appendix 2        Lansky Score

The Lansky score should be used for children <16 years of age.

100 - Fully active, normal

90 - Minor restrictions in physically strenuous activity

80 - Active, but tires more quickly

70 - Both greater restriction of and less time spent in play activity

60 - Up and around, but minimal active play; keeps busy with quieter activities

50 - Gets dressed, but lies around much of the day; no active play, able to participate in all quiet play and activities.

40 - Mostly in bed; participates in quiet activities

30 - In bed; needs assistance even for quiet play

20 - Often sleeping; play entirely limited to very passive activities

10 - No play; does not get out of bed

0 - Unresponsive

Adapted from: [Lansky SB, List MA, Lansky LL, Ritter-Stern C, Miller DR. The measurement of performance in childhood cancer patients. Cancer. 1987 Oct 1;60\(7\):1651-6.](#)

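### Table 5 schedules no Lansky/Karnofsky score at the Off-Treatment Visit, so Arm B completers are not scored after their fifth course (unless they later cross over) while Arm A subjects who reach Cycle 6 are

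*Protocol*

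**What the plan says.** **Randomization Phase.** Protocol Table 5 footnote f states that the Lansky or Karnofsky score "will be obtained at the Screening, Baseline, and C1D1 Visit, and Day 1 of every subsequent cycle visit thereafter". The grid agrees: the row is marked at Screening, Baseline, Day 1 of Cycles 1 to 5 and Day 1 of Cycle 6 onward, with the Off-Treatment and Follow-up cells empty. The rows for pregnancy test, physical examination, vital signs, laboratory tests and urine dipstick are all marked at the Off-Treatment Visit. Footnote g, on the physical examination, names it: "and Day 1 visit of each subsequent cycle, and at the Off-treatment Visit".

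**Extension Phase.** The Table 6 grid marks the score at the Off-Treatment Visit. Its footnote c does not mention that visit: "A Lansky play score or Karnofsky performance status score will be obtained at Day 1 of every cycle visit".

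**Crossover.** Table 7 takes the score at the Off-Treatment Visit in both grid and footnote c: "A Lansky play score or Karnofsky performance status score will be obtained at Baseline, Day 1 of every cycle, and at the Off-treatment visit".

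**Treatment length.** Table 5 footnote o says "Subjects randomized to Arm B will be off-treatment after 5 cycles of ifosfamide+etoposide", while Arm A continues on lenvatinib.

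**Analysis.** Section 9.7.1.8 lists the score among the safety variables presented by treatment group. Section 9.7.1.8.6 says "Lansky play scores or Karnofsky Performance Status score scores will be summarized by shifts from Baseline to worst postbaseline visit". This serves the secondary objective of comparing safety and tolerability between arms (Section 8.2, item 6).

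**The concern.** A worst postbaseline value depends on which visits are scored. In the phase where the arms are compared, the schedule stops at the last Day 1 visit on treatment. That has two consequences.

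First, a Day 1 score can reflect earlier courses but not the one starting that day. Arm B has no Cycle 6, so the fifth course of a completer falls outside the scored window. Arm A subjects who go on to Cycle 6 have that course inside it.

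Second, a subject in either arm who stops mid-cycle, for toxicity or progression, has no score at that point. One who stops during Cycle 1 has none after the first course.

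At stake is the completeness and comparability of one descriptive safety summary. Scores that were never collected cannot be recovered by the analysis plan.

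**Working it through.** The protocol states no figure to reproduce here. The check is of the visit schedule, followed by simple day counts.

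**1. Is the omission real?** The Table 5 header has 20 visit columns: Screening, Baseline, three days in each of five cycles, Cycle 6-X, Off-Treatment and Follow-up. Read against these, the Lansky/Karnofsky, pregnancy-test and physical-examination rows each resolve to 20 cells. The last two carry a mark under Off-Treatment; the performance-score row does not. Footnote f agrees with the grid, so this is not a broken table. Nothing elsewhere restores the score: Section 9.5.1.4 and Section 9.5.5 both refer back to Tables 5 and 6.

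**2. Nominal days.** Inputs: 21-day cycles and an Off-Treatment Visit within 30 days of the final dose (Section 9.1.2.1); chemotherapy on Days 1 to 3. No delays are assumed. Day 1 of cycle k falls on study day 21 × (k − 1) + 1.

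- Cycle 5 Day 1: 21 × 4 + 1 = Day 85 (last Arm B score)
- Last chemotherapy dose: 85 + 2 = Day 87
- Off-Treatment Visit for Arm B: by 87 + 30 = Day 117
- Cycle 6 Day 1: 21 × 5 + 1 = Day 106 (Arm A score after the fifth course)
- Unscored stretch after the last Arm B score: up to 117 − 85 = 32 days

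For an Arm B completer, one of five courses has no later Table 5 score.

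**3. Who is affected?** This illustration takes the assumed medians in Section 9.7.2 (3.5 months in Arm B, 8.75 in Arm A), exponential PFS, 30.4375 days per month and 36 subjects per arm. Stops for toxicity are ignored.

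- Arm B progression-free at Day 85 (2.79 months): 2^(−2.79/3.5) = 0.58, or about 21 of 36
- Arm A progressing before Day 106 (3.48 months): 1 − 2^(−3.48/8.75) = 0.24, or about 9 of 36

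So the differential gap concerns Arm B completers against those Arm A subjects who reach Cycle 6, not the whole arms.

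**4. Stops for toxicity.** In Study 207 (Section 7.3.1), 8 of 31 subjects on the combination stopped for adverse events. At that rate, 36 × 8/31 = 9.3 Arm A subjects would do so. How many would stop between Day 1 visits is not given, so about 9 is an upper illustration. It overlaps with the group in step 3 and must not be added to it.

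**5. Number of scoring occasions.** Arm B has at most 4 scores after Cycle 1 Day 1 (Cycles 2 to 5). An Arm A subject treated to 8.75 months (8.75 × 30.4375 = Day 266) reaches Cycle 13 Day 1 (21 × 12 + 1 = Day 253) and has 12. Adding an Off-Treatment score gives 5 against 13.

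**The case against.** The best case against runs as follows. The Table 5 grid and footnote agree with each other, so leaving out the visit may be deliberate. The score is one of several descriptive safety variables, with no stated test or decision rule. Status at discontinuation is not lost to the trial: the Off-Treatment Visit has a comprehensive physical examination, vital signs, weight and laboratory tests; PedsQL is collected there; and adverse events run to 30 days after the last dose. All of that stands. It limits the importance of the point but does not supply the missing value of this measure.

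Four stronger readings are tempting and are not supported.

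- *Arm B is never scored after its fifth course.* Those who cross over after progression are scored under Table 7, and any still on treatment at the primary cutoff move to Table 6, whose grid includes the visit.
- *Only Arm B loses its last course.* An Arm A subject who stops before Cycle 6 Day 1 also has no score after the last course.
- *The summary is too favourable.* Nothing shows that the missing value would be the worst one. The visit may fall anywhere up to 30 days after the last dose, and the larger number of Arm A scores tends to worsen that arm's worst value.
- *The change of instrument at age 16 calls for keeping the baseline scale.* Inclusion criterion 6 assigns Karnofsky from age 16, and Appendix 2 says "The Lansky score should be used for children <16 years of age". A rule to retain the baseline instrument would contradict both. The documents give no basis for how often the switch would occur, and handling it in a shift table can be left to the SAP.

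**Conclusion.** The point holds as a modest one. Table 5 omits the score at the Off-Treatment Visit in both grid and footnote, unlike the Table 6 grid and Table 7. The by-arm shift to worst postbaseline score therefore lacks end-of-treatment status in both arms. It also leaves out the last course for Arm B completers followed under Table 5, but not for Arm A subjects who reach Cycle 6.

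The day counts assume no delays. Section 9.1.2.1 allows chemotherapy to be resumed later, so actual days will vary. The counts of subjects rest on the sample-size medians and an exponential form, and serve only to show scale. Table 6 supports the point through its grid alone, because its own footnote c leaves the visit out.

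**What to change.** 1. In Table 5, mark the Off-Treatment cell of the Lansky/Karnofsky row and name the Off-treatment Visit at the end of footnote f, as footnote g already does.
2. In Table 6, add the Off-treatment Visit to footnote c so that it agrees with its grid.

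The cost is protocol wording and one brief extra score per subject, at a visit that already includes a physical examination. The gain is an end-of-treatment value in both arms, and a score after the fifth course for Arm B completers. The change does not equalise the number of scoring occasions: that difference comes from the different treatment lengths and should be kept in mind when the shift table is read.

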**Table 5 Schedule of Assessments in Study E7080-G000-230 – Randomization Phase**

Phase	Prerandomization		Randomization a (All cycles are 21 days in duration)																		
	Screening b	Baseline c	Treatment d																Off-Tx	Follow-up	
Period	1	2	3	4	5	6	7	8	9	10	11	12	13	14	15	16	17	18+			
Visit			Cycle 1			Cycle 2			Cycle 3			Cycle 4			Cycle 5				Cycle 6-X		
Cycle			1	8	15	1	8	15	1	8	15	1	8	15	1	8	15	1			
Day	-28 to -2	-1																			
Procedures/Assessments																					

- h. Assessments will include vital signs (resting BP, HR, RR, and body temperature) and weight. Blood pressure that is consistently above the 95th percentile for sex, age, and height/length for subjects <18 years old; or BP  $\geq$ 140/90 mmHg for subjects  $\geq$ 18 to 25 years old requires further evaluation. Refer to hypertension management guidelines in [Section 9.4.1.1.2](#).
- i. On Cycle 1 Day 8, subjects will have a telephone or clinic visit to assess for the development of early toxicity. Subjects will be provided with a BP cuff to monitor BP at home or can have the measurement done by a local healthcare provider, and will report the C1D8 measurement at telephone contact. An unscheduled visit can occur prior to C1D15 if deemed necessary by the investigator.
- j. Single 12-lead ECG. If possible, subjects must be in the recumbent position for a period of 5 minutes prior to the ECG. ECG should be conducted at Screening, C1D1, C2D1, D1 of every 4th cycle (ie, C6, C10, C14, etc.). ECG at C1D1 and C2D1 should be conducted approximately 2 hours after lenvatinib dose. For high risk subjects (as defined in lenvatinib product label), conduct ECG in every cycle.
- k. An echocardiogram or MUGA scan is to be performed during screening, every 16 $\pm$ 2 weeks, and at the Off-Treatment visit, or sooner if clinically indicated.
- l. Clinical chemistry and hematology results must be reviewed by the investigator prior to administration of study drug on C1D1 and within 48 hours after administering any study drug for all subsequent cycles. Electrolytes such as potassium, calcium, and magnesium should be monitored and abnormalities, when considered clinically significant, should be corrected in all participants before starting treatment. Scheduled assessments may be performed within 72 hours prior to the visit. If  $\geq$ Grade 3 hematologic or clinical chemistry toxicity, repeat laboratory test and AEs assessment at least every 3 days (until improvement to <Grade 3). TSH should be assessed for all subjects. For sites in Germany: HIV and Hepatitis B/C tests are required during Screening.
- m. Urine dipstick testing should be performed at Screening, Baseline, C1D15, C2D1, C2D15, and Day 1 of every subsequent cycle, or more frequently as clinically indicated, and at the Off-treatment Visit. For subjects with a history of proteinuria  $\geq$ 2+, urine dipstick testing should be performed until the results have been 1+ or negative for 2 treatment cycles. If a new event of proteinuria  $\geq$ 2+ occurs, refer to [Section 9.4.1.1.4](#) for further management guidelines. Urine glucose should be performed as part of the urine dipstick.
- n. Sampling (one 2 mL sample per time point) for PK analysis of lenvatinib will be performed (in subjects in Arm A only) on Cycle 1 Day 1 at 0.5 to 4 hours and 6 to 10 hours postdose, on Cycle 1 Day 15 at predose, 0.5 to 4 hours and 6 to 10 hours postdose, and on Cycle 2 Day 1 at predose. All predose samples are to be drawn approximately 24 hours following the dose administered on the previous day. If dose interruption is necessary at these time points, please contact the sponsor. Pharmacokinetic sampling should not be performed for any subject with a body weight <13 kg (please see [Section 9.5.1.3.1](#)).

